#### **5.4. Safety**

This study will be conducted in accordance with the principles of Good Clinical Practice (GCP) as outlined in the Declaration of Helsinki and the International Conference on Harmonization.

The principal investigator of the study will review study related events for adjudication.

All efforts will take place to ensure patient safety. Each patient will be monitored for safety throughout the trial utilizing clinical evaluations and laboratory markers. Laboratory markers and/or clinical evaluations that are out of normal range will be recorded as adverse events and reviewed with the investigator.

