Objectives	

• The primary objective is to establish a baseline profile for individual healthy study subjects using various modalities and monitor them longitudinally to identify deviations that develop over time and may be relevant to human health and longevity. The secondary objective is to identify the modality that has the highest impact on the identification of deviations from baseline profile.

Adverse Event (AE) Monitoring	Adverse events associated with the study procedures, of venipuncture, non-invasive imaging and functional tests will be reported, although they are expected to be limited due to the nature of these common procedures.

Inclusion Criteria	To participate in the study, patients must meet the following criteria;						
	
 
1. Male or non-pregnant female; age 18 to 90.
 
2. Absence or presence of any medical history or any signs or symptoms of any disease.
 
3. Women of childbearing potential (WOCBP) must have a negative urine pregnancy test (UPT) at all visits.
 
						
Exclusion Criteria	Patients who meet any of the following criteria will be excluded from study participation;						
	
 
1. Unwillingness or inability to participate in the study
 
2. Unwillingness or inability to provide written Informed Consent Form
 
3. WOCBP with positive pregnancy test at enrollment or at any visit
 
						
Study Schedule	Event	Baseline Visit	6-Month Visit $\pm$ 1month	12-Month Visit $\pm$ 1month	18-Month Visit $\pm$ 1month	24-Month Visit $\pm$ 1month	36-Month Visit $\pm$ 1month
	Informed Consent	X					
	Review of Inclusion/Exclusion Criteria	X					
	Medical history and physical exam	X	X	X	X	X	X
	UPT for WOCBP	X	X	X	X	X	X
	Whole Genome Sequencing Analysis	X					
	Biochemical/Omics Analysis	X	X	X	X	X	X
	Non-Invasive Imaging	X	X	X	X	X	X
	Functional Assessments (as needed)		X	X	X	X	X
	Wearables and Quantified Self Assessments (as needed)		X	X	X	X	X
	Adverse Event Monitoring	X	X	X	X	X	X

1. UPTs must have a minimum sensitivity of 25 mIU  $\beta$ -hCG/mL.

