##### 3.2.1. Inclusion Criteria

- Male or non-pregnant female; age 18 to 90
- Absence or presence of any medical history or any signs or symptoms of any disease
- Women of childbearing potential (WOCBP) must have a negative urine pregnancy test (UPT) at all visits.

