##### 3.2.3 Participant withdrawal criteria

A participant may be withdrawn from the study prior to completion for any of the following reasons:

- Adverse Event (AE)
- Death
- Physician decision
- Pregnancy at any visit
- Protocol deviation
- Other (e.g., any reason that may affect the outcome of the study or safety of participants)
- Participant no longer wants to participate (without penalty)

When a participant is withdrawn from the study for an AE (as defined in Section 5), when possible, the participant should be followed until resolution or stabilization of the AE.

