## 5. Adverse Events

### 5.1. Definitions

An Adverse Event (AE) is a noxious and unintended event observed in, or reported by, a participant who is participating in (or has participated in) a clinical study, and/or received study medication, an experimental device, or study-related procedure. The event may be related temporally either to immediate or long-term use of a drug, device, or procedure. It may not necessarily be caused by a drug, device, or procedure. Any event meeting these criteria shall be considered an adverse event, regardless of whether or not it is considered study related. A pre-existing condition that worsens during the trial is considered an AE.

The following events will be considered as adverse events:

- Event directly related to study procedure
- Unintended event as a result of non-standard of care study tests, medications or procedures

A Serious Adverse Event (SAE) is defined as one that is fatal or immediately life-threatening, severely or permanently disabling, requires or prolongs in patient hospitalization, a congenital anomaly, cancer or overdose (intentional or accidental); or suggests a significant hazard, contraindication, side effect, or precaution. All SAEs will be followed by the investigator through trial end until resolution or until reaching a clinically stable status per the investigator's discretion.

The following adverse events will be handled as serious even if they do not meet the above criteria for designation as serious:

- Death
- Congenital abnormality
- Hospitalization
- Life threatening illness
- Intervention to prevent permanent damage

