### 5.3. Reporting

The Puer study does not prescribe any pharmaceutical or medical device-based intervention. Any AEs are associated with blood draw/venipuncture and MRI examinations that may or may not include Gadolinium-based contrast agents will be reported.

Each patient will be observed and queried in a nonspecific fashion at each contact during the study for any new or continuing symptoms since the last contact. All adverse events will be reported on the appropriate CRF. Details will include the type of event, date of onset, duration, intensity, causality relationship to the study procedure (if applicable), and outcome. Wherever possible, a diagnosis rather than symptom(s) will be reported.

If an AE should occur, every attempt will be made to obtain as much information as possible about event evaluation and outcome. Documents of this follow-up will be maintained with the patient's study records.

If a SAE occurs, the participation in the study will be interrupted or discontinued at the investigator's discretion.

All protocol deviations will be reported to the WCG IRB.

All SAEs will be reported immediately to the WCG IRB and the FDA (if applicable).

Endpoints will be adjudicated by the Principal Investigator. A written report detailing the endpoint adjudication will be provided by the Principal Investigator.

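### Section 5.4 makes every out-of-range result an adverse event, including stable abnormal values present at entry, which do not fit the definition in Section 5.1

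*Protocol*

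**What the plan says.** Section 5.4 (Safety) gives the recording rule: "Laboratory markers and/or clinical evaluations that are out of normal range will be recorded as adverse events and reviewed with the investigator". The rule has no qualifier, and no other section supplies one.

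Section 5.1 (Definitions) begins: "An Adverse Event (AE) is a noxious and unintended event observed in, or reported by, a participant". On existing disease it adds: "A pre-existing condition that worsens during the trial is considered an AE". It then lists two kinds of event that count: those directly related to a study procedure, and unintended results of study tests, medications or procedures outside standard care. It does not say whether the list is exhaustive.

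Section 3.2.1 admits adults aged 18 to 90 with "Absence or presence of any medical history or any signs or symptoms of any disease". The schedule in the Protocol Synopsis marks both biochemical/omics analysis and AE monitoring at baseline and at the 6-, 12-, 18-, 24- and 36-month visits.

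Section 1.2 (Rationale) argues for judging laboratory values against the participant's own history over time and not against population cut-points.

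**The concern.** A site that applies Section 5.4 as written must open an AE record for a laboratory value that was abnormal before the study began and has not moved. A site that applies Section 5.1 would not. Both rules sit in the section that is meant to define an AE for the whole study.

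Two things are at stake. The first is the meaning of the AE data. The study exposes participants to contrast agents, ionising radiation and venipuncture, and the AE record is where harm from these would be seen. Filling it with entry status makes that harm harder to pick out. The second is workload and uniformity. Each AE carries the CRF details required by Section 5.3 and the duty there that "If an AE should occur, every attempt will be made to obtain as much information as possible about event evaluation and outcome". With up to 20 sites, some may follow the literal rule and others the definition, and their AE data would then not be comparable.

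**Working it through.** The protocol gives no figure on this point, so there is nothing to reproduce. The check sets the rules side by side for one case: a participant with known, stable disease whose laboratory value is out of range at baseline and unchanged afterwards.

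1. **Section 5.4.** The value is out of normal range, so it is recorded as an AE. The investigator's review is an added step and does not filter what is recorded.
2. **Section 5.1, general definition.** A stable value that reflects a condition brought into the study is not a noxious and unintended event. Not an AE.
3. **Section 5.1, pre-existing conditions.** The condition has not worsened, so this sentence does not bring it in.
4. **Section 5.1, waiver of causality.** Study relatedness is not required, but only for events that already meet the section's criteria. This value does not, so the waiver does not help.
5. **Section 5.1, two-item list.** The value was neither caused by a procedure nor an unintended result of a study test. It falls outside the list, whether the list is read as examples or as the full scope.
6. **Can the case arise?** Yes. Section 3.2.1 allows any disease at entry, and laboratory work and AE monitoring are both marked at all six visits, the first being baseline. No separate safety panel is defined that would confine Section 5.4 to a few tests. The laboratory assessments are those of Section 3.3.2.
7. **Can a site use its own judgement?** Not within the text. Section 8.4 accepts no deviations, and Section 5.3 sends every deviation to the IRB. Leaving out a stable baseline value departs from Section 5.4.
8. **Fit with the rationale.** Section 1.2 makes the participant the reference. Section 5.4 uses the normal range and does not mention the participant's baseline.

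Steps 1 and 2 to 5 give opposite answers for the same value.

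Size: the number of AEs that would arise this way depends on how many markers are measured, how often each is out of range, and how repeated findings are grouped. The protocol gives none of these.

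**The case against.** The strongest reply is that Section 5.4 is a deliberate, conservative capture rule. Section 5.1 does not say that a pre-existing condition is an AE *only* if it worsens, so Section 5.4 can be read as adding to the definition. That stands as far as it goes: a reader might infer that Section 5.1 limits AEs to what is new or worsened, and it contains no such general test. But if Section 5.4 is an addition, Section 5 still holds two tests with different answers, and nothing says which governs.

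The protocol also has safeguards. The CRF records intensity, causality and outcome; Section 5.3 prefers a diagnosis to separate symptoms; the principal investigator reviews study-related events for adjudication; Section 6 calls for quality assurance of AE reporting; and baseline results are kept as source data. These allow much to be sorted out later and soften the loss. Most act only after the entry has been made, and none removes the conflict over what to enter.

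Three stronger readings are tempting and are not supported:

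- **Lost follow-up.** A reader might infer that over-recording leads to withdrawals, because AE is a listed reason in Section 3.2.3 and Section 7 uses data only up to withdrawal. Section 3.2.3 is permissive, and nothing links an out-of-range result to withdrawal.
- **Conflict with the synopsis.** The synopsis says AEs "will be reported, although they are expected to be limited due to the nature of these common procedures". That sentence concerns AEs of venipuncture, imaging and functional tests. It makes no forecast about out-of-range results.
- **A large numerical burden.** With an assumed 20 to 100 markers, each out of range with probability 1% to 5%, the share of participants with at least one such value at baseline is 1 − (1 − p)^k if markers are independent: 1 − 0.99^20 = 18% up to 1 − 0.95^100 = 99%. With perfectly correlated markers it is p itself, 1% to 5%. A range from 1% to 99% built on assumptions supports nothing.

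**Conclusion.** The point holds on the text. Section 5.4 records every out-of-range laboratory or clinical value as an AE, and for a stable abnormal value present at entry this does not fit Section 5.1. The conclusion needs no numerical assumption. It rests on the unqualified wording of Section 5.4, on the absence of an exception elsewhere, and on entry criteria and a schedule under which such values must be expected.

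The consequence is limited. The study is descriptive and makes no formal hypothesis tests, and AE counts are not among its endpoints. The harm is to the clarity and comparability of the safety data and to site workload, and its size cannot be derived from the protocol. It should be corrected because it is a stated rule that gives a wrong record when obeyed, and the correction loses no data.

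The AE scope statements in Section 5.3 and the synopsis also name different procedures. That is a separate, minor matter of wording and adds nothing to this conclusion.

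**What to change.** Reconcile Section 5.4 with Section 5.1 so that Section 5 holds one AE test:

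- Keep all out-of-range laboratory and clinical values as study data.
- Record values already out of range at the baseline visit as baseline data.
- Record a laboratory or clinical value as an AE only when it meets the reconciled Section 5 definition.
- State in that definition how a value is compared with the participant's own baseline. Mark this as a clarification, since Section 5.1 does not now contain it.
- Print the same instruction on the AE CRF for all sites.

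Section 3.2.3 already refers to Section 5 for the meaning of an AE, so it would take up the reconciled definition.

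Costs: a protocol amendment, which Section 8.3 requires to be reviewed and approved before it is implemented, and one CRF instruction. Some investigator judgement enters, and it may vary across sites; the common instruction limits this but does not remove it. AE records from before and after the change will not be directly comparable unless earlier entries are re-classified, which the baseline laboratory data already collected should allow. In return, sites have fewer AE records to complete and follow up.

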## 6. Data Management

Following completion of the consenting process (including informed consent and Authorization for Use/Disclosure of protected health information (PHI)) and it has been determined that the patient meets all of the inclusion and none of the exclusion criteria, enrollment will occur, and data collection will commence.

A secure Electronic Data Capture (EDC) and data management system will be used for entry, storage, review, and management of study data. The system will be compliant with applicable GCP and regulatory requirements. Investigators are responsible for accurate completion and timely submission of the data collected during the study. Sites will be trained in the use of the EDC system for entering study data and uploading supporting documents and will be given access for this purpose.

Quality assurance procedures will be established to ensure that complete, accurate and timely data are submitted, protocol requirements are followed, and that AEs are correctly reported. The management and retention of these data will be compliant with applicable regulatory requirements.

### 6.1. Case Report Forms

All required data for this study will be collected on standardized paper CRFs. The research staff will review completed CRFs to attest that all data entered on them are complete and accurate.

Medical history, demographics, hospital, office, and research records for any visit (including any notes, reports, test results, and lab reports from the clinical evaluation, biochemical and “omics” assessment, non-invasive imaging, functional assessments, and wearable/quantitative self-assessments) are considered source documentation and will be collected and reviewed to confirm clinical events and may be utilized for data analysis. Data will be collected on all patients and entered into a CRF.

The Investigator or designee will be responsible for completing, in a timely manner, the CRF for each participant related to previously reported or newly detected AEs. And end of study withdrawal form will also be included as part of the CRF.

### 6.2. Database

Data from the CRF will be transcribed to the EDC system. Data collected for omics and imaging will be retained with 3rd parties conducting these analyses.

### 6.3. Safeguarding of Genomic Data

Some blood samples will be used for genetic testing. There are laws that protect participants from discrimination based on their genetic information. A Federal law called the Genetic Information Nondiscrimination Act (GINA) makes it illegal for health insurance companies, group health plans, and most employers to discriminate against individuals based on their genetic information. GINA does not protect against genetic discrimination by companies that sell life insurance, disability insurance, or long-term care insurance. GINA also does not protect against discrimination based on an already-diagnosed genetic condition or disease. In some cases, employers could use genetic information to decide whether to hire or fire an individual. There is a risk that someone could get access to participant

genetic information and identify them by name. Puer Research will protect these data in the study and will not share or sell these data to outside parties without participants' written consent.

#### **6.4. Quality Control**

PUER Research will fulfill the responsibilities identified in their standard operating procedures. These responsibilities include collecting and tracking data forms and instituting quality control measures for data entry verification and study compliance. Puer Research or its designee will be responsible for auditing the database and confirming the overall integrity of the data. Puer Research or its designee will ensure that all information pertaining to significant new developments and unanticipated AEs are provided to the appropriate regulatory authorities, the Investigators, and to the WCG IRB.

Monitoring of the study will be conducted at regular intervals in order to monitor study conduct and maintain GCP by periodic review of the data in the EDC. These inspections are conducted in order to verify adherence to the protocol and the completeness and accuracy of the data being entered into the CRF.

## 7. Statistical Considerations

By design, the study will not employ formal hypothesis testing. Study endpoints will be described using descriptive statistics, using means and standard deviations, medians with inter-quartile ranges, and other descriptive statistical methods, as appropriate.

Data from participants who discontinue the study prior to completion will only be considered through the date of withdrawal and will not be followed in the remaining longitudinal study endpoints.

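### Section 7 stops all endpoint follow-up at discontinuation, and an admission can be the event that leads to discontinuation, so the exploratory 24- and 36-month admission counts can be cut short by the outcome itself (minor)

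*Protocol*

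**What the plan says.** Section 7 fixes what happens to data after discontinuation: "Data from participants who discontinue the study prior to completion will only be considered through the date of withdrawal and will not be followed". The rule covers every longitudinal endpoint still outstanding and makes no exception for endpoints that need no study procedure.

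Section 2.4 lists, as exploratory endpoints, the numbers of unscheduled admissions and of unscheduled urgent care or emergency visits within 24 and 36 months of enrollment.

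Section 5.1 defines an SAE to include an event that "requires or prolongs in patient hospitalization, a congenital anomaly, cancer or overdose", and lists hospitalization again among the events handled as serious. Section 5.3 adds: "If a SAE occurs, the participation in the study will be interrupted or discontinued at the investigator's discretion". Section 3.2.3 names an adverse event (AE) among the reasons for withdrawal.

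After withdrawal for an AE, Section 3.2.3 keeps one kind of follow-up: where possible, "the participant should be followed until resolution or stabilization of the AE". Section 5.1 likewise has the investigator follow each SAE until it resolves or is clinically stable. Both concern the event itself, not the study endpoints.

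The protocol disagrees with itself on which events are AEs:

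- Broad: Section 5.1 counts events "regardless of whether or not it is considered study related".
- Narrow: the list that follows in Section 5.1 begins with "Event directly related to study procedure" and has one further item, on unintended results of study tests, medications or procedures.
- Narrow: the synopsis says "Adverse events associated with the study procedures, of venipuncture, non-invasive imaging and functional tests will be reported", and the first paragraph of Section 5.3 says "Any AEs are associated with blood draw/venipuncture and MRI examinations" will be reported.

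**The concern.** Read together, these sections let the outcome being counted stop its own counting. A person admitted at month 8 and then discontinued contributes that admission and nothing more, although the endpoint runs to month 36. People who are admitted once are plausibly at higher risk of another admission, so the lost time would fall mainly on those with most events to lose.

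A crude count per enrolled participant is then too low. A crude person-time rate is also too low if risk differs between people, because high-risk people leave early and low-risk people supply most of the follow-up time.

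Urgent visits are affected only indirectly. A visit without admission is not a listed SAE, but visits after an admission-driven exit are lost too.

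**Working it through.** **The chain of text.** (1) An admission is an endpoint event (Section 2.4). (2) It is also an SAE, at least on the broad reading (Section 5.1). (3) Participation may then be discontinued (Sections 3.2.3, 5.3). (4) Discontinuation ends endpoint follow-up (Section 7). (5) What follow-up remains is of the triggering event only. Each step is in the protocol. Step 3 is discretionary, and an interruption alone does not reach step 4.

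**No stated figure to reproduce.** The protocol gives no admission rate, dropout rate or share of admissions leading to exit. Everything below is assumed for illustration.

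**Hand-checkable case.** Let admissions be Poisson at rate λ per year, let each end participation with probability π, and assume no other dropout. The expected counted admissions over T years are (1 − exp(−λπT))/π, against λT with full follow-up.

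- With λ = 0.1, π = 0.25, T = 3: (1 − e^(−0.075))/0.25 = 0.289 against 0.300, a 3.7% undercount.
- With gamma variation between people (variance v = 2, that is shape 0.5): (1 − (1 + vλπT)^(−1/v))/π = (1 − 1.15^(−0.5))/0.25 = 0.270, a 10.0% undercount.

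**Adding ordinary dropout.** Let other dropout have hazard δ = 0.10 per year and let λ be gamma-distributed between people with mean 0.1 or 0.2 and shape 0.5 (strong variation) or 2 (weak). With total exit hazard h = δ + πλ:

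- expected count = E[λ(1 − e^(−hT))/h]
- expected person-time = E[(1 − e^(−hT))/h]

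Other dropout alone (π = 0) gives a shortfall of 1 − (1 − e^(−0.3))/0.3 = 13.6% at 36 months. That is not this mechanism and is subtracted. The shortfall added by admission-driven exit at 36 months, in percentage points (mean λ 0.1 / 0.2), is:

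| Share of admissions ending participation | Shape 0.5 | Shape 2 |
|---|---|---|
| 1% | 0.37 / 0.73 | 0.18 / 0.37 |
| 2% | 0.73 / 1.45 | 0.37 / 0.73 |
| 5% | 1.80 / 3.52 | 0.91 / 1.81 |
| 10% | 3.52 / 6.73 | 1.81 / 3.55 |
| 25% | 8.24 / 14.89 | 4.40 / 8.41 |

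At 24 months the additions are 0.13 to 1.04 points for 1–2% and 3.18 to 11.31 points for 25%.

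**Crude person-time rate at 36 months.** This is low by 0.07 to 1.12% for 1–2% and by 1.72 to 11.72% for 25%. If everyone has the same risk, it is unbiased.

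**Model-based rate.** A negative binomial model with observed follow-up time was fitted to simulated data (3,000,000 participants, T = 3, π = 0.25, relative standard error 0.09 to 0.15%):

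- Exit depends only on recorded admissions, gamma variation: within 0.2% of the truth.
- The same, but true variation is lognormal: low by up to 1.8%.
- Exit depends on unrecorded risk at the same intensity: low by 1.6 to 9.1%.

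**Narrow AE reading.** If 1% of admissions are procedure-related and 25% of those end participation, the effective π is 0.01 × 0.25 = 0.0025. The addition at 36 months is then 0.05 to 0.18 points.

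Urgent visits were not modelled.

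**The case against.** The strongest reply has four parts.

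1. **The chain is permissive.** Nothing requires exit after an admission. The study prescribes no intervention and admits people with or without any disease, so an unrelated admission gives little reason to stop. High exit shares such as 25% have no support in the text. This stands, and it is why the low end of the table deserves most weight.

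2. **It is largely an analysis matter.** Section 7 leaves room for other descriptive methods, and a rate model using observed follow-up nearly removes the bias when exit depends only on recorded admissions. This stands for the mean rate, if the model is right. It does not restore admissions that were never collected, and it fails if exit also depends on risk that is not recorded. A statistical analysis plan cannot undo a protocol rule that stops collection.

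3. **The chain depends on which AE definition applies.** On the narrow reading it all but vanishes. This also stands. But the broad reading has real support: beyond the sentence in Section 5.1, Section 5.3 has participants queried nonspecifically and all AEs reported, and Section 5.4 records out-of-range findings as AEs with no condition on relatedness.

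4. **The consequence is small.** The endpoints are exploratory, there is no comparison arm and no hypothesis test. Under the same assumptions, ordinary dropout costs more than this mechanism in every cell of the table except the 14.89-point one. This stands and sets the grade.

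**Conclusion.** The concern holds as a possibility written into the protocol: an admission can lead to discontinuation, and Section 7 then ends collection of the very events being counted. In the scenarios examined the bias in the crude count is always downward. Its size cannot be established from the protocol. Under the assumptions stated it is at most about 1.4 points at 36 months if 1–2% of admissions end participation, 0.9 to 3.5 points at 5%, and up to 14.9 points only with a 25% exit share, the higher admission rate and strong variation in risk. On the narrow AE reading it is negligible. The issue is minor: only exploratory endpoints of a descriptive study are shown to be affected. Confidence is medium, because both the exit share and the intended AE scope are unknown.

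**What to change.** Amend Section 7 so that stopping study procedures does not by itself end outcome collection. Unscheduled admissions, urgent visits and vital status would continue to be collected, from records or by contact, to month 36 unless the participant withdraws consent. The consent form and the authorization for use of health information need matching text.

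Reconcile the synopsis and Sections 3.2.3, 5.1, 5.3 and 7 on which events are AEs or SAEs and on what discontinuation ends. The investigator's decision after an SAE is not touched by this.

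The cost is protocol wording, consent and authorization text, and site effort for those participants who discontinue without withdrawing consent. Section 6.1 already treats hospital and office records as source documents, so no new data source is needed. Deviations that can be found only by study imaging or omics are not recovered this way.

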### 2.3. Exploratory Objectives:

- To assess the impact of introducing leading-edge scientific methods on the number of medications and/or dietary supplements taken by individuals
- To assess the impact of leading-edge scientific methods on the number of *unscheduled* health care visits

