### 2.4. Exploratory Endpoints

[figure not shown]
- The number and change in the number of medications taken by an individual at 6 months, 12 months, 18 months, and 24 months after enrollment
- The number and change in the number of dietary supplements taken by an individual at 6 months, 12 months, 18 months, and 24 months after enrollment

- Number of unscheduled, urgent care/emergency department visits within 24 months and 36 months after enrollment
- Number of unscheduled hospital admissions within 24 months and 36 months after enrollment

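### Unscheduled visits and admissions are plain counts within 24 and 36 months, but leavers' data stop at withdrawal and no time at risk is stated, so dropout can make the means too low

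*Protocol*

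**What the plan says.** Protocol Section 2.4 lists two utilisation endpoints: "Number of unscheduled, urgent care/emergency department visits within 24 months and 36 months after enrollment" and "Number of unscheduled hospital admissions within 24 months and 36 months after enrollment". Both are numbers over a fixed window, with no rate or denominator. They serve the exploratory objective in Section 2.3, which reads "To assess the impact of leading-edge scientific methods on the number of" unscheduled health care visits.

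Section 7 plans no formal hypothesis testing. It summarises endpoints "using means and standard deviations, medians with inter-quartile ranges" and leaves room for other descriptive summaries. Its rule for early leavers has two parts. The first is "Data from participants who discontinue the study prior to completion will only be considered through the date of withdrawal". The second is that these participants "will not be followed in the remaining longitudinal study endpoints".

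Section 3.2.3 opens its list with "A participant may be withdrawn from the study prior to completion for any of the following reasons", and death is on that list. The Section 7 rule therefore covers deaths as well as withdrawals by participant or physician.

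**The concern.** A number within 36 months presumes 36 months of observation. Someone who leaves at month 8 supplies events from 8 months only. If that count enters a 36-month mean as it stands, the unobserved 28 months are treated as 28 months without a visit. This happens even when leaving has nothing to do with health care use.

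The second part of the Section 7 rule allows another reading, in which a leaver is dropped from later endpoints and only completers are summarised. The text does not say which is meant, and the two readings give different numbers from the same data.

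The population makes this more than a formality. Section 3.2.1 admits ages 18 to 90 with or without disease, and follow-up runs to 36 months, so some deaths should be expected. With no hypothesis test, the descriptive figure is itself the result on which the Section 2.3 objective will be judged.

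**Working it through.** **Inputs.** The windows of 24 and 36 months come from Section 2.4. Truncation at withdrawal comes from Section 7. The Synopsis gives 36 months of enrollment and a 72-month study. Since 36 + 36 = 72, every participant can reach month 36, and only withdrawal or death shortens observation. The protocol states no attrition rate and no visit rate, so it has no figure of its own to reproduce. Two assumptions are therefore needed: attrition of 2% to 20% per year, and a constant visit rate of 0.5 per person-year for illustration.

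**Reading A: truncated counts kept, averaged over all enrolled.** For annual attrition d, unrelated to the visit rate:

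- Hazard: h = −ln(1 − d)
- Mean time observed to year t: (1 − exp(−ht))/h
- Mean count: 0.5 × that time, against 0.5 × t under full follow-up
- Shortfall: 1 − (1 − exp(−ht))/(ht), which does not depend on the visit rate

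At d = 10%, h = 0.10536. Mean time to 24 months is (1 − 0.81)/0.10536 = 1.803 of 2 years, a shortfall of 9.8%. Mean time to 36 months is (1 − 0.729)/0.10536 = 2.572 of 3 years, a shortfall of 14.3%.

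| Attrition per year | Mean years observed of 2 | 24-month mean (true 1.00) | Too low by | Mean years observed of 3 | 36-month mean (true 1.50) | Too low by |
|---|---|---|---|---|---|---|
| 2% | 1.960 | 0.980 | 2.0% | 2.911 | 1.455 | 3.0% |
| 5% | 1.901 | 0.950 | 5.0% | 2.781 | 1.390 | 7.3% |
| 10% | 1.803 | 0.902 | 9.8% | 2.572 | 1.286 | 14.3% |
| 20% | 1.613 | 0.807 | 19.3% | 2.187 | 1.093 | 27.1% |

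**Reading B: completers only.** This was simulated with 1,000,000 participants whose visit rates vary by a gamma factor with mean 1 and variance 1.

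- Attrition unrelated to the visit rate: completers' means are about 1.00 and 1.50, the true values. There is no artefact.
- Attrition hazard proportional to the visit rate (10% per year at the average rate): completers' means are 0.824 and 1.138. The shortfalls are 1 − 0.824 = 18% and 1 − 1.138/1.50 = 24%.

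As a check on the last line, the mean factor among completers is 1/(1 + ht). That is 1/1.2107 = 0.826 at 24 months and 1/1.3161 = 0.760 at 36 months, giving means of 0.826 and 0.760 × 1.50 = 1.140, in line with the simulation.

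**Events per person-year.** With attrition unrelated to the visit rate, events divided by time at risk return 0.50 at both windows for every attrition rate tried. With attrition proportional to the visit rate, at 10% per year, the rate is 0.454 at 24 months and 0.437 at 36 months. That is 1 − 0.454/0.50 = 9% and 1 − 0.437/0.50 = 13% too low. The bias is smaller than under Reading B, but it is not removed.

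**The case against.** The strongest reply is that Section 7 does not fix the error. Its second clause can be read as removing leavers from the 24- and 36-month endpoints, and ordinary dropout then does no harm. It also leaves room for other descriptive summaries, so a rate is not excluded, and an analysis plan that is not at hand may specify one. This stands to the extent that the protocol states no time at risk but does not forbid one. It does not remove the point. The completers-only reading excludes deaths and early leavers and is biased if heavier users leave. For a cumulative count, the first clause more naturally keeps the truncated data. Neither reading of the stated rule is safe.

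A reader might go further and infer that dropout would show up as a fall in unscheduled visits, to be taken as a benefit of monitoring. Divided by nominal time at 10% attrition, the counts would indeed show 0.475 in year 1 and 0.384 in months 24 to 36 against a flat true rate of 0.50. The protocol plans no such comparison. Cumulative counts in a fixed cohort cannot fall between 24 and 36 months. No yearly or pre-enrollment contrast is defined, and no change is defined for visits, unlike medications: "The number and change in the number of medications taken by an individual at 6 months, 12 months, 18 months, and 24 months after enrollment". So the supportable claim is an undercount.

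Nor does this extend to the main endpoints on new deviations. Those are stated at timepoints, and nothing here shows them to be affected.

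Death also needs separate care. A deceased participant's count is complete up to death, so the loss is one of interpretation: a short life reads as low use unless deaths are shown beside the counts. Listing death as a withdrawal reason does not prevent this, since Section 5.1 handles death as a serious event.

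**Conclusion.** The point holds as an undercount that depends on how Section 7 is read. If truncated counts are averaged over everyone enrolled, the means are too low by 2.0% to 19.3% at 24 months and by 3.0% to 27.1% at 36 months, for assumed attrition of 2% to 20% per year. These figures rest on a constant visit rate and attrition unrelated to it. They describe means only; the effect on medians was not calculated. If only completers are summarised, unrelated attrition gives no bias. Attrition that rises with health care use lowers the means, by 18% and 24% in the 10% scenario above.

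Severity is minor. The endpoints are exploratory and descriptive, and no test depends on them.

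**What to change.** In Section 7, state that unscheduled visits and admissions will be summarised as events per person-year for all enrolled participants, with time at risk ending at withdrawal, death or the window limit, whichever comes first. Show the mean cumulative count to 24 and 36 months with death as a terminal event, and the number of deaths alongside. This also settles whether leavers stay in these summaries.

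The cost is a few sentences and slightly more analysis work. The withdrawal date is already needed to apply the Section 7 rule, Section 6.1 includes a withdrawal form in the case report form, and deaths are captured as serious events.

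The rate removes only the artefact of dropout unrelated to visits. Bias from outcome-related dropout remains and should be stated as a limitation.
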